10.2 INTERIM ANALYSIS

Throughout the study, enrollment rates, heart failure event prevalence, and adherence will be analyzed.

Additionally, at 100 enrolled patients with approximately 90 day follow up, an interim analysis may be performed. Data will be shared with Bodyport for statistical analysis and possible publication. Bodyport will use the scale biomarker data to validate a model that reflects changes in patient status. The model will use intra-patient biomarker trends to detect meaningful deviations from a patient's baseline state.

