2. BACKGROUND AND TRIAL RATIONALE

2.1 BACKGROUND INFORMATION

Heart failure (HF) is a major health, social and economic problem worldwide.¹ The incidence and prevalence of HF are increasing,² in part due to an aging population and rising burden of comorbidities.³ Efforts to decrease mortality, decrease hospitalization rates and improve the well-being of patients with HF were modestly successful over the last decade with the introduction of medical therapies and care strategies.⁴ However, despite advances in medical and device therapies, the number of hospitalizations for HF and associated readmissions remains high and represents an increasingly unsustainable financial burden.⁵ As a result, reducing HF readmission rates has become a priority in many of the developed countries. In the US alone, the costs related to HF are expected to reach \$70 billion by 2030, an increase of 130% on current costs.⁶⁻⁸

Achieving and maintaining an euvolemic status is a key goal in the management of HF. Thus, close observation of, and rapid response to changes in early physiological indicators are essential in achieving or maintaining euvolemia. Clinical signs and symptoms of HF decompensation are preceded by an increase in filling pressures, autonomic adaptation and resultant cardiac function and total fluid content changes.

The Bodyport Cardiac Scale provides an innovative and noninvasive approach to obtain clinically relevant hemodynamic parameters. The Bodyport Cardiac Scale is a physical platform in which the user stands with bare feet. The scale captures a number of physiological parameters including weight, electrocardiogram, impedance plethysmography and ballistocardiography to derive a proprietary

algorithm to monitor for cardiac decompensation through a preceding change in heart rate, cardiac output, stroke volume, cardiac time intervals, body weight and other biomarkers. Bodyport Cardiac Scale biomarkers are transmitted to a HIPAA-compliant cloud via an integrated cellular LTE-M modem for storage and visualization in a web-based application. The simplicity of the Bodyport Cardiac Scale enables patients to use the system at home, allowing patients to be monitored remotely and make treatment decisions with their medical team without the need for an in-person visit.

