3. OBJECTIVES AND ENDPOINTS

3.1 PRIMARY OBJECTIVES

The primary objective of this study is to utilize data from the Bodyport Cardiac Scale to develop an algorithm that allows for the early detection of worsening HF.

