4.1 OVERALL STUDY DESIGN

SCALE-HF 1 is a prospective, multicenter study. The overarching goal is to enroll a broad population of patients with HF and follow them remotely for clinical events. Patients will be identified by participating sites and may be consented and enrolled remotely, in clinic, or prior to hospital discharge. Follow-up visits will be remote and occur at 6 weeks, 3 months and then every 3 months until the end of the study. Follow-up information will be collected by sites and may be supplemented by a centralized telephone call center (and email) via trained personnel at the Duke Clinical Research Institute. Participants may also be contacted by the site and/or study team at other timepoints for study issues such as suspected device malfunction or nonadherence with the Bodyport Cardiac Scale.

Patients eligible for the study will have HF and a prior history of hospitalization for acute decompensated HF. A history of clinical HF will be confirmed by site investigators. To ensure that a broad population of patients is enrolled, there will be limited additional inclusion and exclusion criteria. The participant population is described in more detail in Section 5 below.

All patients will consent for longitudinal follow-up. This will include remote follow-up visits as well as access to clinical records to evaluate for future clinical events. The remote follow-up visits will place a minimal burden on patients and sites and be limited to assessments for suspected clinical events. All patients will consent to release of medical records regarding HF history and suspected clinical events. Based on site- and participant-reported events, medical records for possible clinical events will be collected. Possible clinical events will be reviewed and adjudicated by a clinical events committee using standardized definitions. The committee members will be blinded to sensor and algorithm data.

Training on device use will be provided to patients and daily utilization of the Bodyport Cardiac Scale will be requested. Device sensor data will be uploaded remotely and analyzed on an ongoing basis throughout the study. Patients, study teams, and treating clinicians will be blinded to the investigational sensor data other than basic information that is currently available through other devices including weight, heart rate and leg edema status. There will be no attempt to utilize the study data to influence clinical practice.

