10.3 SAMPLE SIZE

Data derived from this study will add to the model development aims of the Bodyport Cardiac Scale. This study is statistically powered to detect approximately 75 primary endpoints which will approximate to about 300 enrolled patients. An event rate of 75 equates to an approximate rate of 25% at 6 months. Given that this study is a development study however additional events may be required to derive the predictive algorithm.

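### Does calling the optional 100-patient interim a validation contradict a protocol whose aim is to develop the algorithm?

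*Protocol*

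**What the plan says.** Section 10.2 (Interim Analysis) makes the look optional: "at 100 enrolled patients with approximately 90 day follow up, an interim analysis may be performed". It continues: "Data will be shared with Bodyport for statistical analysis and possible publication". It then gives the purpose: "Bodyport will use the scale biomarker data to validate a model that reflects changes in patient status". The sentence after that describes the model as one that follows each patient's own biomarker trends and flags departures from that patient's baseline. Section 10.2 names no performance measure, no reference standard and no decision that depends on the result.

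Elsewhere the language is that of development. Section 3.1 (Primary Objectives) aims "to develop an algorithm that allows for the early detection of worsening HF". Section 10.3 (Sample Size) adds: "Given that this study is a development study however additional events may be required to derive the predictive algorithm". Section 10.1 describes selecting features associated with heart failure events, combining them into a model with an alert algorithm, and optimizing on sensitivity and specificity. Earlier in section 10.1, validation of the model is mentioned in passing, beside feature extraction, as something that follows signal cleaning.

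**The concern.** In prediction work, validating a model normally means testing one that was fixed beforehand on patients who played no part in building it. Section 10.2 does not say where the interim model comes from or whether it is fixed before these patients' outcomes are seen. If it is the same algorithm that the study is still building, *validate* claims more than sections 3.1 and 10.3 allow, and it would do so on a small fraction of the events that section 10.3 already regards as possibly too few.

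What is at stake is the description of a published interim result. A development result presented as validation would overstate the evidence, and a performance estimate from a dozen or so events would be very imprecise.

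**Working it through.** **Inputs, all from the protocol.** About 300 patients, about 75 events and 25% at 6 months (section 10.3); 100 patients with about 90 days of follow-up (section 10.2); 6 months of enrollment (Protocol Summary).

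**1. The protocol's own figure.** 300 × 0.25 = 75. It reproduces.

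**2. Events at the interim if each patient contributes exactly 90 days.** Six months is taken as 182.6 days.
- Linear accrual: 100 × 0.25 × 90/182.6 = 12.3.
- Constant hazard: 100 × (1 − 0.75^(90/182.6)) = 13.2.
- Share of 75: 12.3/75 = 16.4% and 13.2/75 = 17.6%.

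**3. How firm that count is.** Section 10.2 does not say that follow-up is truncated at 90 days.
- Assuming even accrual, 300/6 = 50 patients enroll per month. The 100th enrolls at month 2.0 and reaches 90 days (2.96 months) at month 4.96.
- The first 100 then have 2.96 to 4.96 months of follow-up, with a mean of 3.96. Expected events: 100 × 0.25 × 3.96/6 = 16.5, or 22% of 75.
- If everyone enrolled by then were used: 50 × 4.96 = 248 patients, 248 × 4.96/2 = 615 person-months, and 615 × 0.25/6 = 25.6 events.
- The count also moves with the shape of the risk. If 60 to 70% of the 6-month events fell in the first 3 months, 100 patients would give 25 × 0.6 = 15 to 25 × 0.7 = 17.5. If the 25% accrued over 9 months at constant hazard, 100 × (1 − 0.75^(3/9)) = 9.1.

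The plausible range for 100 patients is therefore about 9 to 17.5, and 12 to 13 is one case within it.

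**4. What such counts would mean for precision.** This is an illustration only, because the protocol states no sensitivity. Detecting 9 of 13 events has an exact 95% interval of about 39 to 91%; 52 of 75 has about 58 to 79%. These intervals apply only if the interim model is scored against heart failure events, which section 10.2 does not say.

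**5. The passages side by side.**
- *Is it the same model?* Section 10.3's caution concerns the predictive algorithm, and section 10.1 builds that algorithm on association with heart failure events. Section 10.2's model flags departures from a patient's own baseline. The two may be one object at different stages, or two different objects. If they differ, comparing the interim count with 75 is not a like-for-like comparison.
- *Might a model already exist?* Section 10.3 opens: "Data derived from this study will add to the model development aims of the Bodyport Cardiac Scale". That fits work already under way before this study. Section 2.1 refers to a proprietary "algorithm to monitor for cardiac decompensation through a preceding change in heart rate" and other measures, and section 4.1 says of the adjudicators: "The committee members will be blinded to sensor and algorithm data". None of this proves that a fixed model exists, but all of it is compatible with one. In that case *validate* is a fair word.
- *Validated against what?* The secondary objectives compare scale data with implantable sensors, invasive hemodynamics, biomarkers and blood volume analysis. A deviation model could be checked against these, and the number of heart failure events would then not be the limiting quantity. The text neither confirms nor excludes this.
- *How strictly is the word used?* Section 10.1 places model validation among ordinary processing steps. Read that way, section 10.2 makes no claim of independent validation.

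A conflict arises only if the interim model is assumed to be the event algorithm, still unfixed, and the word is taken in its strict sense. The document establishes none of these three conditions.

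**The case for a change.** The best case for a change is that the mismatch lies in the protocol's own sentences. A statistical analysis plan could set out when the model is locked, yet section 10.2 would still say *validate* while sections 3.1 and 10.3 speak of developing and deriving. Section 10.2 is also the section that mentions publication, so the label could reach readers who never see section 10.3. The loose use in section 10.1 can be turned round: a second undefined use is a reason to define the term. The repair would take one or two sentences.

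Part of this stands. The origin of the interim model is unstated, and anyone publishing the interim should say whether the model was fixed beforehand. That statement belongs with the reported result, however, and depends on what is actually done at an analysis that may never take place. Fixing a model version before an optional look is commonly left to the statistical analysis plan, which is not at hand here. The small number of events does not strengthen the case, since section 10.2 does not tie the model to those events.

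**Conclusion.** This is a real ambiguity of wording, but no contradiction has been shown and no change to the plan is needed. The label is fair if an existing fixed model is tested and loose if the model is still being built, and the protocol supports either reading. The arithmetic is sound on its assumptions: about 12 to 13 events if follow-up is cut at 90 days, about 16.5 if the first 100 patients are followed to the data cut under even accrual. It does not show an error, because section 10.2 sets neither the cut nor the outcome against which the model is judged.

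The consequence is limited to how an optional, possibly published result is described. No stopping rule, sample size, endpoint or final analysis depends on it. Clarifying section 10.2 would only record which activity the interim is, a gap that analysts can fill when they carry out and report it. This judgment assumes that the interim stays without decision consequences, as section 10.2 describes it.

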10.3 SAMPLE SIZE

Data derived from this study will add to the model development aims of the Bodyport Cardiac Scale. This study is statistically powered to detect approximately 75 primary endpoints which will approximate to about 300 enrolled patients. An event rate of 75 equates to an approximate rate of 25% at 6 months. Given that this study is a development study however additional events may be required to derive the predictive algorithm.

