Population:	 Approximately 300 male and female participants in the US, 18 years of age or older, irrespective of left ventricular ejection fraction with symptomatic HF will be enrolled. Patients must be able to stand independently on the Bodyport Cardiac Scale. We will exclude patients with a weight > 170 kg, prior heart transplant or currently listed for heart transplant, current LVAD, current inotropes, and end-stage renal disease requiring chronic dialysis.
Sites Enrolling	Approximately 5 US sites
Participants:	
Duration of Study	Approximately 1 year (6 months enrollment and approximately 6 months follow up)
Study Product	Bodyport Cardiac Scale

Figure 1. SCALE-HF Overall Design. Scale-HF 1 will be the first in a series of studies that aims to evaluate the use of the Bodyport Cardiac Scale to rapidly identify early worsening HF in order to allow for clinical interventions to prevent disease progression.

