10. STATISTICAL METHODS AND DATA ANALYSIS

10.1 STATISTICAL AND ANALYTICAL PLANS

The Bodyport Cardiac Scale captures various physiological signals including an electrocardiograph, an impedance plethysmograph, and a ballistocardiograph. These raw signals will be filtered and interpolated prior to feature extraction and model validation. Regions with motion artifacts or noise will be identified and removed. Ensemble average waveforms will be constructed from the real-time signals. Specific characteristic features will be identified on the averaged waveforms. Temporal and amplitude-based biomarkers will be extracted from the identified features within and across each averaged waveform. These features and biomarkers will be assessed longitudinally by constructing trends consisting of multiple measurements and identifying statistically significant changes over time. Some of the key features being explored in this study are: weight, heart rate, heart rate variability, peripheral impedance, body fluid, balance, stroke volume, cardiac output, pre-ejection period, left ventricular ejection time, as well as the amplitude and timing of characteristic features on the IPG, ECG, and BCG signals. A focus on these specific features is driven by prior research demonstrating clinical relevance to cardiovascular function and heart failure status.

During analysis, various methods will be implemented to select signal features that demonstrate a meaningful association with HFEs. Those features most strongly correlated to HFEs will be combined into a model and associated alert algorithm. The development of the model may use a combination of techniques, including multivariate regression and machine learning (e.g. support vector machines, clustering, decision trees, Bayesian networks). Models will be evaluated and optimized based on their sensitivity and specificity to detect heart failure events.

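### Does calling the study powered for about 75 endpoints, without a hypothesis or power figure, leave its sample size unsupported?

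*Protocol*

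**What the plan says.** Section 10.3 of the protocol gives the whole sample-size argument in a few lines. It states: "This study is statistically powered to detect approximately 75 primary endpoints which will approximate to about 300 enrolled patients". It then supplies the planning rate: "An event rate of 75 equates to an approximate rate of 25% at 6 months". It closes with a caveat: "Given that this study is a development study however additional events may be required to derive the predictive algorithm".

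Three other places bear on how to read this.

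- The primary objective in Section 3.1 is "to utilize data from the Bodyport Cardiac Scale to develop an algorithm that allows for the early detection of worsening HF". This is a development aim, with no comparison and no hypothesis.
- Section 10.1 gives the criterion for judging models: "Models will be evaluated and optimized based on their sensitivity and specificity to detect heart failure events". No target value or interval width is named. The section's only reference to significance is to "identifying statistically significant changes over time" in biomarker trends, with no level and no link to the 75.
- The Protocol Summary plans 6 months of enrolment and about 6 months of follow-up, which fits a 6-month rate. Sections 4.1 and 6.2 run the follow-up contacts until the end of the study.

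**The concern.** A study has power to reject a stated null hypothesis, or to reach a stated precision. It does not have power to detect a number of events. A reader who takes Section 10.3 at its word will look for a hypothesis, an alpha, a power and an effect size, and the protocol has none of them for the 75.

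Read more generously, the sentence might promise that 75 endpoints will be reached. At the protocol's own rate that promise looks weak, because the expected count is 75 and the chance of falling short is close to one half. No allowance for loss to follow-up is stated either.

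At stake would be the only justification given for enrolling about 300 people. An ethics board, or a reader of the published results, might think the size rests on a formal power calculation when it rests on an expected count. The section also leaves open whether 75 counts patients with a first event or all events.

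**Working it through.** **Inputs.** From Section 10.3: about 300 patients, about 75 primary endpoints, 25% at 6 months. From the Protocol Summary: 6 months of enrolment and about 6 months of follow-up. The protocol gives no alpha, hypothesis, power, effect size, precision target or dropout allowance, so no power formula can be applied.

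**Step 1: the plan's own figure.** Expected count = N x p = 300 x 0.25 = 75. In reverse, 75 / 0.25 = 300. The figure reproduces exactly.

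**Step 2: the chance of reaching 75.** Assume one counted event per patient, complete 6-month follow-up and a true risk of exactly 25%. The count X is then Binomial(300, 0.25), with standard deviation sqrt(300 x 0.25 x 0.75) = 7.5.

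- P(X >= 75) = 0.522, so P(X <= 74) = 0.478.
- The 2.5% and 97.5% quantiles are 61 and 90.
- P(X >= 70) = 0.767, P(X >= 69) = 0.806 and P(X >= 65) = 0.921.

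The 52% follows from quoting a mean. The mean of a binomial count of this size sits almost at its median, so any study that states its expected count will reach it about half the time.

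**Step 3: how far that probability depends on assumptions the protocol leaves open.** Each row changes one feature of Step 2.

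| Reading | Expected count | P(75 or more) |
|---|---|---|
| First events, exactly 6 months, no loss | 300 x 0.25 = 75 | 0.52 |
| 25% is an event rate, patients counted (constant rate assumed) | 300 x (1 - e^(-0.25)) = 66.4 | 0.13 |
| 25% is a risk, all events counted (constant rate assumed, Poisson) | 300 x (-ln 0.75) = 86.3 | 0.90 |
| First events to a common close, Weibull shape 0.5 | 88.6 | 0.96 |
| First events to a common close, Weibull shape 1.0 | 104.5 | above 0.999 |
| 5% of patients contribute no events (assumed) | 285 x 0.25 = 71.25 | 0.33 |
| 10% of patients contribute no events (assumed) | 270 x 0.25 = 67.5 | 0.16 |

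The common-close rows fix the risk at 25% at 6 months and assume uniform accrual over 6 months and no loss, so follow-up runs from 6 to 12 months. The expected count is 300 times the average, for t from 6 to 12, of 1 - 0.75^((t/6)^k), where k is the Weibull shape.

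The probability runs from 0.13 to above 0.999 according to reading. It measures the assumptions more than any defect in the design. The expected counts themselves stay between about 66 and 105.

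**Step 4: what depends on the word.** Section 10.1 builds and tunes models on sensitivity and specificity. Nothing there, in the interim look of Section 10.2 or in the endpoint definition of Section 3.2 uses a power figure or a threshold of 75. With a different verb in Section 10.3, every patient, measurement and analysis would be the same.

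**The case for a change.** The strongest case for acting is that this is an affirmative statement in the protocol, not a silence that an analysis plan could fill. It claims statistical adequacy and, two sentences later, concedes that the number may not be enough for the primary objective. The caveat says more events may be needed to derive the algorithm. It does not say that 75 is only an expectation. Sample-size wording also tends to be repeated in registry entries and papers, and rewording would cost almost nothing.

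Part of this stands. The word is wrong as a technical term, the counting unit is unstated, and no precision or model-development reason is given for aiming at 75. But the sentence says approximately 75, not at least 75, and the next one sets out the rate behind it, so a reader can see at once that the number is 300 times 25%. A development study needs no hypothesis test, so the missing alpha and power are not faults in themselves. Reading the sentence as a guarantee of 75 adds something the text does not say.

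**Conclusion.** No change to the plan is needed. Section 10.3 uses the language of power loosely for an expected count. That is a slip of wording, and the numbers behind it are sound: 75, 300 and 25% at 6 months agree exactly, and the 6-month basis matches the planned follow-up. The protocol states no power that the design then fails to deliver.

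The 52% chance of 75 or more, and the 61 to 90 range, hold only if each patient is counted once, follow-up is complete to 6 months and the true risk is 25%. Under other readings the chance lies anywhere from about 0.13 to above 0.999, so it cannot be used to call the study too small. Whether 75 counts patients or events can be settled when results are reported. The caveat that more events may be required already tells the reader how firmly to take the number. Correcting the word would alter nothing that the study does, estimates or concludes.
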